### The NEVR device:

The device to be used in this protocol (NEVR) is an integration of 3 components: 1) QUASAR's 24 channel dry EEG headset (DSI-24), 2) the HTC Vive, and 3) an alpha -activity-based NF protocol. (Figure 1) The DSI-24 is a dry electrode EEG headset that is sold commercially as a research device, while the HTC Vive VR headset is sold commercially as a consumer device. Integration of both hardware devices will include the addition of harnesses to improve comfort and distribution of weight while wearing both devices.

**Electrical Safety:** Safety considerations for the dry electrode EEG sensors and DSI-24 headset have been addressed by testing and certifying the device according to the Electromagnetic Compatibility Directive (EMC) testing according to ETSI EN 301 499-1 (2011/09) V1.9.2 and ETSI EN 301 499-17 (2012/09) V2.2.1; the Low Voltage Directive (LVD) testing according to EN 61010-1:201. During the set-up of the headset, contact between the electrodes and the skin is assessed via a measurement of the contact impedance. To accomplish this, a very small current is applied to the skin. According to the ANSI/AAMI EC38:1998 safety standard, which is the applicable medical standard, the direct current through the patient-electrode connection should not exceed 0.1  $\mu$ A. Our system exposes subjects to a current of 0.0012  $\mu$ A, far below this safety threshold. For comparison, holding a 1.5V AAA battery would result in a current of 0.75  $\mu$ A, or 700 times that of our system.

**Figure 1. NEVR Hardware components: A) QUASAR DSI-24 EEG headset; B) HTC Vive Virtual Reality (VR) headset; C) DSI-24 headset work with a VR headset.**

### **NF Protocol:**

During each session, subjects will sit in a comfortable seat, and the experimenter will place the headset, which requires no skin abrasion nor the application of any conductive gels. Set-up time is ~5-15 minutes depending upon the hair type of the participant. Our headsets are designed with mechanical adjustments to fit a wide range of heads (52-62 cm in circumference) and the electrodes are double spring loaded in order to provide comfortable contact against the scalp. Once the headset is placed, the experimenter will work each electrode through the subject's hair to ensure good contact with the scalp, and adequate signal quality as determined by measurement of contact impedance and visual inspection of EEG traces respectively. Once electrode impedances are within the recommended range for the DSI-24 (<1MOhm), and EEG traces show no traces of electrical or motion artifacts, recordings will be initiated.

The first recordings will consist of 2-minute Eyes Open (EO) and Eyes Closed (EC) tests in order to calibrate each individual. Once those recordings are complete, the NF protocol will begin. This protocol involves watching a VR Movie (which the subject can choose from a selection of PG-13 choices). The NF protocol entails extracting alpha activity levels from the EEG signal, setting individual thresholds, and modulating video replay or gaming experience based on the patient ability to increase his or her alpha levels to a target range. When alpha activity falls below the threshold, the video may pause, and/or its brightness/sounds may dim, or a game may progress. Subjects will be given the opportunity to rest between the 5-minute blocks.

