## 9. RESEARCH DESIGN AND METHODS

This will be a single arm clinical trial with up to 25 subjects undergoing NF training in VR using the NEVR prototype and protocol. This is a feasibility study where only one arm (NF group) is needed for demonstration of feasibility; the number of subjects is based on a recently published study by Mayaud et al. 2019.

Each patient will be recruited from [name] patient population, and after signing informed consent will undergo a cognitive and behavioral pain assessment followed by 20 NF sessions, every other day or 3 times per week. Each session will take up to 1 hour and will consist of: donning of NEVR system, recording EEG while subjects sit with their Eyes Open then Eyes Closed for EEG threshold calibration, followed by performing six 5-minute blocks of NF. Subjects will then be asked to conduct a brief usability survey after each session. At the end of the 20 sessions, subjects will undergo the same cognitive and behavioral assessment conducted at the study's onset.

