### **Statistical Analyses:**

**EEG:** QUASAR will analyze the EEG data to track changes in alpha activity over the course of the treatment and correlate those to the clinical outcomes. Change in Alpha activity will be calculated between the first and last EEG recordings after the 20 sessions. Furthermore, QUASAR will review the data to determine the minimal subset of electrode locations that would yield reliable detection of alpha activity needed for this NF protocol.

**Behavioral and Cognitive outcomes:** QUASAR will conduct statistical analysis of the results of the pain assessments conducted prior to and after treatment with paired t-test or Wilcoxon signed-rank tests to determine the effects of the treatment (both across the first and last sessions and across the entire 20 sessions). In addition, QUASAR will correlate the clinical outcome measures to the EEG results using cross-correlation analyses and Wilcoxon signed-rank test and will account for multiple comparisons according to the methods described in Mayaud et al, 2019.

**Questionnaires:** Usability survey results will be tabulated and analyzed by QUASAR to inform the design of

the Phase II device.

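### The feedback rule lists a game moving forward as a response to low alpha, which on its ordinary reading contradicts the stated aim of raising alpha; the two sentences need reconciling

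*Combined protocol and SAP*

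**What the plan says.** The feedback rule is in the NF Protocol subsection of section 9 (Research Design and Methods). The mode introduced first is a film: "This protocol involves watching a VR Movie (which the subject can choose from a selection of PG-13 choices". The next sentence describes the principle as setting individual alpha thresholds and "modulating video replay or gaming experience based on the patient ability to increase his or her alpha levels to a target range". That sentence names both modes and gives one direction for both, namely upward. The sentence after it gives the operational rule: "When alpha activity falls below the threshold, the video may pause, and/or its brightness/sounds may dim, or a game may progress".

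The overview at the start of section 9 says where the threshold comes from ("recording EEG while subjects sit with their Eyes Open then Eyes Closed for EEG threshold calibration") and that each session has six 5-minute feedback blocks. It gives no feedback rule of its own. The Statistical Analyses subsection then uses the trained quantity as an outcome: "Change in Alpha activity will be calculated between the first and last EEG recordings after the 20 sessions". The same subsection plans to correlate the EEG results with the clinical outcome measures.

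**The concern.** In neurofeedback, the intervention is the link between the measured signal and what the subject sees or hears. The operational sentence attaches three responses to a single condition, alpha below threshold. Two of them interrupt or degrade the experience when the subject misses the target. The third advances the experience at the same moment. Read in the ordinary way, the film would encourage higher alpha and a game would encourage lower alpha, although the sentence before gives one direction for both.

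If game mode were used on that rule, the alpha change from first to last recording would no longer reflect one training direction, and neither would its correlation with pain and function. The study has a single arm of up to 25 subjects, so there is no comparison group to help separate a weak training effect from feedback that pulled in two directions. A reader or replicator also could not tell from the protocol what feedback game-mode subjects received.

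**Working it through.** No plan figure is at issue and no sample-size or error-rate calculation applies. The check compares each listed response with the stated aim.

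**Step 1: the aim.** The principle sentence in NF Protocol asks subjects to increase alpha to a target range, in video and in game. Alpha below threshold therefore means that the target is not being met.

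**Step 2: the responses to alpha below threshold.**

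| Listed response | Ordinary effect on the subject | Agrees with the aim of raising alpha? |
|---|---|---|
| Video pauses | Experience interrupted | Yes |
| Brightness or sound dims | Experience degraded | Yes |
| Game moves forward | Experience advances | No |

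The third row rests on an inference that moving forward in a game is a reward. The protocol does not define it. It is the natural meaning beside pausing and dimming.

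**Step 3: does another section settle it?** The overview in section 9 covers calibration and the number of blocks. The device subsection says only that the feedback protocol is based on alpha activity. No section states a separate rule for games, says what happens above threshold, or gives game progression another meaning. Individual calibration sets where the threshold lies, not which way the feedback acts.

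**Step 4: how much feedback could be affected?** Each subject is due 20 sessions × 6 blocks = 120 blocks. The documents do not say how many of these, if any, use a game, so the number could be anywhere from 0 to 120.
- At 0, the contradiction has no effect on the data.
- At 120, with the sentence followed literally, all feedback for that subject would run against the stated aim.
- In between, the two directions would be mixed within the subject.

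Turning this into a loss of alpha change would also need the training effect per block in each mode. The protocol gives no expected alpha change and no variability for it. Its sample size rests on a citation alone ("the number of subjects is based on a recently published study"). The size of the effect therefore cannot be computed.

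**The case against.** The best defence is that the direction is already fixed. The principle sentence covers games as well as video, and the sentence after it reads as an illustration in permissive language. A dropped clause about alpha above threshold would explain the wording completely. Much of this stands: a drafting slip is likely, and a sensible operator would probably follow the stated aim. It does not remove the point, because the illustrative sentence is the only operational statement of the rule and, as written, it permits a response that contradicts the aim.

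Four stronger readings are tempting, and the documents support none of them.

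- **That the device trains alpha the wrong way in games.** The feedback protocol is listed as a component of the device, but its programming is not described. Nothing says that staff set the feedback from this sentence.
- **That opposite directions are mixed within the arm.** The film is the only mode that subjects are said to use. Games appear only in the two sentences compared here, and no section describes a game or a choice between modes.
- **That the dilution can be quantified.** A percentage would need an invented share of game blocks and an assumption that training in the two modes is equal and opposite. The documents supply neither.
- **That the alpha results would be uninterpretable and should be reported by mode.** Alpha change is a planned analysis but is not named in Aim 1, which concerns the effect of training on pain impact, together with feedback surveys. The plan computes one first-to-last change per subject, and that change cannot be divided between modes for a subject who used both. The documents also do not say that the mode goes unrecorded.

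**Conclusion.** The contradiction is real and lies between two adjacent sentences of the NF Protocol subsection. On its ordinary reading, one of the three responses to low alpha runs against the other two and against the stated aim, and nothing elsewhere resolves it. It is an error in the description of the intervention, not merely missing detail, and it should be corrected.

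The harm is conditional. It arises only if a game is used, the sentence is followed as written, and progression acts as a reward. The alpha-change measure and its correlation with clinical outcomes would then be blurred by an amount that the documents do not allow anyone to estimate. If no game is used, those analyses are untouched and only the wording needs repair.

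**What to change.** Reconcile the two sentences in NF Protocol. For each feedback mode, state the response when alpha is below threshold and when it is above, so that both agree with the training aim that the protocol already gives. If games will not be used, saying so and removing them from the subsection would also resolve the contradiction.

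If game mode is used at all, note the mode in the session log as a descriptive item, so that readers can see what was delivered. No analysis by mode is needed.

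The cost is a short wording change and at most one log field. No visits, subjects or assessments are added. The correction is best made before sessions begin, because a mode that is not logged at the time may not be recoverable later.

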### **Pain Assessments:**

Pain assessment will be conducted prior to and after the first, 10th and last sessions via all of the following battery of standardized subjective, objective, behavioral and functional evaluation tests:

2) Numerical Rating Scale (NRS, or Visual Analog Pain Score (VAS);

Pain scores are measured using a visual analog scale. This consists of a 10 cm line with "no pain" written at one end and the "worst imaginable pain" written at the other end. The patient is asked to place a mark along the line that corresponds with their pain. The distance, in cm, from the no pain end to the location of the mark gives a measurement of the pain. Subjects will be asked to rate their spontaneous pain and evoked pain to movement.

4) The DALLAS scale;

A self-reported disability scale for patients with low back pain assessing the impact on everyday quality of life: work and leisure, anxiety, depression, and sociability; each subpart varies from zero to one hundred percent.

12) Patient Assessment Global Change; and

The patient assessment global change is a 2-item measure assessing individuals perceived improvement following treatment.

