**6. SPECIFIC AIMS**

**Aim 1: Validate NEVR on patients with FBSS:** 20 chronic back pain patients will be recruited at UCSD and undergo 20 sessions of NF training with the NEVR prototype. Their pain impact will be assessed through an extensive cognitive and functional battery before and after the first and last NF sessions, along with feedback surveys.

**Aim 2: Define the system specifications and design the Phase II system:** QUASAR will analyze the collected EEG data to determine the minimal subset of electrodes that would be necessary to reliably measure alpha activity in this population. QUASAR will then review the user feedback and develop system specifications and a concept design for a new headset to be built under Phase II.

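### The global-change measure is scheduled before session 1 and sent to a paired test, although it has no pre-treatment value

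*Combined protocol and SAP*

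**What the plan says.** The Pain Assessments part of Section 9 sets the timing for the battery as a whole: "Pain assessment will be conducted prior to and after the first, 10th and last sessions via all of the following battery". No instrument has its own schedule. Two of the listed instruments matter here.

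- The global-change measure: "The patient assessment global change is a 2-item measure assessing individuals perceived improvement following treatment".
- The Dallas scale, a self-reported disability scale "assessing the impact on everyday quality of life: work and leisure, anxiety, depression, and sociability". Each part is scored from zero to one hundred percent, and no recall period is given.

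The Statistical Analyses part of Section 9 takes the assessments made before and after treatment and applies "paired t-test or Wilcoxon signed-rank tests to determine the effects of the treatment". It names two kinds of comparison, one across the first and last sessions and one across all 20 sessions, and exempts no instrument.

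The schedule is described differently in two other places. Aim 1 in Section 6 puts the assessments "before and after the first and last NF sessions, along with feedback surveys", with no mention of session 10. The opening of Section 9 describes one assessment before the 20 sessions, after which, at the end, "subjects will undergo the same cognitive and behavioral assessment conducted at the study's onset". On session length it says "Each session will take up to 1 hour".

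**The concern.** A paired test needs two measurements of the same quantity, one before and one after. A rating of perceived improvement since treatment is itself a before-to-after comparison, made by the patient. Asked before any treatment, it refers to nothing.

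An analyst following the plan literally must improvise. One choice is to use whatever patients wrote before session 1. Another is to substitute a no-change value as baseline, which quietly turns the paired test into a one-sample test of the later rating. A third is to leave the measure out. The plan does not say which, and the choice could be made after the data are seen. The resulting p-value could also be presented as a pre/post treatment comparison, which it would not be.

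The Dallas scale raises a milder question. It describes work, leisure, mood and social life. If it is compared before and after a single session, the two answers are about an hour apart, and little of what it asks about takes place in between.

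**Working it through.** The plan gives no effect size, standard deviation, significance level or power for this measure, so there is no stated figure to reproduce. The check is whether each planned pair has two meaningful members.

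**Administrations.** Pain Assessments: 3 sessions (first, tenth, last) × 2 (before, after) = 6. Aim 1: 2 sessions × 2 = 4. Opening of Section 9: 2, at onset and at the end. All three descriptions include an assessment before session 1.

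**Global-change measure.** Of the 6 administrations, 1 (before session 1) precedes all treatment and has no meaningful value. Statistical Analyses can be read in two ways, so both are shown.

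| Contrast | Reading | Status for the global-change measure |
|---|---|---|
| Before vs after session 1 | within-session | undefined |
| Before vs after the last session | within-session | computable, but compares two change ratings |
| Before session 1 vs before the last session | first vs last session | undefined |
| After session 1 vs after the last session | first vs last session | computable, but compares two change ratings |
| Before session 1 vs after the last session | whole course (both readings) | undefined |

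Under either reading, 2 of the 3 contrasts (two from that reading plus the whole-course one) are undefined. The third compares two change ratings and does not estimate change from baseline. The whole-course contrast, which matters most, is lost under both.

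**Dallas scale.** The contrast from before session 1 to after the last session has two valid members. Only contrasts within a session, at most about 1 hour apart, are hard to interpret.

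**What a stand-alone report would show.** The exact (Clopper-Pearson) 95% limits for x improved out of n are the 2.5% point of Beta(x, n − x + 1) and the 97.5% point of Beta(x + 1, n − x). Aim 1 gives 20 patients. Section 10 gives at most 25 enrolled with 10% to 50% dropout, so completers range from 25 × 0.5 = 12.5 to 25 × 0.9 = 22.5. Assuming, for illustration, that half report improvement:

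- 6 of 12: 21% to 79%
- 10 of 20: 27% to 73%
- 11 of 22: 28% to 72%

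These intervals describe precision only. The 50% is an assumption, not a forecast.

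**The case against.** The strongest reply is that the measure's own definition already points to use after treatment, so sensible staff would not ask it at baseline and the analyst would not pair it. That is likely in practice, and it keeps the point small. It does not remove it: the schedule applies to the entire battery, the opening of Section 9 calls the final assessment the same as the one at onset, and no separate rule for this measure appears anywhere.

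It can also be said that testing a change rating against no change is a legitimate one-sample analysis. That is true, but it is not the analysis written down.

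On the Dallas scale, the objection largely succeeds. The phrase about the first and last sessions may mean session 1 against the last session. The within-session reading is the more natural one, because Aim 1 speaks of before and after those sessions and the two named comparisons would otherwise nearly repeat each other, but it remains an inference.

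Three stronger readings are tempting, and the documents do not support them.

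- A reader might infer that Dallas scores cannot change within an hour. No recall period is given, and self-reports, notably of anxiety and depression, can shift on immediate re-administration through mood, expectation or retest noise. Only the interpretation as everyday disability fails.
- A reader might try to put a false-positive rate on a substituted no-change baseline. The documents give neither a response scale nor a standard deviation. Such a calculation would only return the power of a one-sample test under an assumed shift, and a genuine improvement of that size would give the same number.
- A reader might count the surplus tests and quote a familywise error rate. Only some battery items are visible in the text available for review, subscales of one instrument in the same patients are not independent, and Statistical Analyses mentions a multiplicity adjustment, though it may cover only the correlations with EEG.

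**Conclusion.** The point holds for the global-change measure. As written, the plan collects it once when it can have no meaning and applies a paired test that is undefined for session 1 and for the whole course. This follows from the plan's own definition and schedule and needs no outside assumption.

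The Dallas point is secondary and depends on within-session contrasts being intended. If they are, a within-session difference should not be interpreted as a change in everyday disability. The comparison across the course is unaffected.

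Severity is minor. This is a single-arm feasibility study, the VAS comparisons and the whole-course Dallas comparison stand, and no usable data are lost. No error rate is attached to the problem, because the documents do not give the figures needed to calculate one.

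**What to change.** 1. In Pain Assessments, collect the 2-item global-change measure only after session 10 and after the last session.
2. In Statistical Analyses, remove it from the paired tests and report it as a stand-alone post-treatment outcome, for example the proportion reporting improvement with an exact 95% confidence interval. Define in advance how the two items are combined or reported separately, and which responses count as improvement. State that in an open single-arm study this does not remove expectation or courtesy bias.
3. Say what the comparison across the first and last sessions means. If it is within-session, limit it to momentary measures such as the VAS.
4. Test the Dallas scale only across the course, from before session 1 to after the last session. Keep the administration after the last session, because collecting it only before that session would lose the end-of-course value.
5. Reconcile the schedules in Aim 1, the opening of Section 9 and Pain Assessments into one table of instruments by time point.

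The cost is protocol and analysis wording, with slightly less questionnaire burden on patients. No change to sample size or visits is needed.
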